6.0 STUDY PLAN

6.1 SUMMARY OF STUDY PLAN

Pre-adolescent and AYA patients with newly diagnosed HR-ALL will have dietary and activity preferences assessed by a registered dietician (RD) and physical therapist (PT) at the start of induction.

Subjects will receive an individualized comprehensive dietary and physical activity plan. The RD and PT will devise a personalized dietary and activity intervention aimed at creating a minimum 10% caloric deficit each day (10% nutritional + exercise) throughout the four weeks of induction therapy. Adherence to the intervention will be assessed by the RD and PT at regular weekly intervals at routine clinic visits for chemotherapy and with home phone-calls between clinic visits. Home and hospital activity will also be recorded using a wearable electronic movement monitoring device (Fitbit ®) for all participants. A list of representative “menu” of possible activity interventions from which subjects may choose is provided as a separate Appendix. The primary efficacy of the intervention will be assessed in comparison to a recent historical control via determining the change in body fat percentage (and lean muscle) during induction as quantified by dual-energy x-ray absorptiometry (DXA). A key secondary aim will be the effectiveness of the intervention to reduce chemoresistance as evidenced by decreased prevalence of leukemia minimal residual disease (MRD) at the end of induction. MRD using multicolor flow cytometry is routinely assessed as a predictor of outcome in all patients with HR-ALL. Exploratory analyses will also examine biomarkers of the proposed mechanism including adiposity and intervention-related changes in leukemogenic signaling pathways, oxidative stress, and cellular metabolism. Parent- and subject-reported QOL assessments will consist of the PedsQL and Child and Adolescent Scale of Participation (CASP) surveys (see separate Appendix) and will be conducted pre- and post-induction and at two delayed time-points (mid-point of intensive chemotherapy [3 months from diagnosis] and at end of intensive chemotherapy phase [10 months from diagnosis] to assess the psychosocial benefits of the intervention.

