11.3 POTENTIAL RISKS OF INTERVENTION

We do not anticipate any risks directly due to the dietary intervention. Subjects may be at risk for syncope, falling and injury during the activity intervention. The PT will design an activity intervention for each subject that will aim to reduce the risk of fall and injury in patients that experience or develop minor difficulties balancing. In-hospital activity interventions will be properly supervised by a PT with vast experience handling pediatric cancer patients undergoing therapy. The potential risks of home-based

activities and methods for reducing risks will be discussed with patients and their families. Changes in weight and body composition are being carefully monitored by both a RD and PT throughout the intervention. Subjects that are unable to adhere to the dietary and/or activity intervention may be at risk for psychological distress (i.e. depression, anxiety, etc.). The treatment team will work to proactively address these risks in each patient through positive discussion and adjustment of the intervention if necessary. Additionally, each patient may be at risk for psychological distress following the introspective nature of the QOL assessment. Psychological distress from any facet of the intervention will be monitored by the treatment team and referred to the psychosocial team if necessary.

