12.0 CRITERIA FOR REMOVAL FROM THERAPY AND OFF-STUDY CRITERIA

12.1 OFF-THERAPY CRITERIA

1. Continuation of the intervention is determined by physician judgment to not be in the best interest of the patient
2. Subject refuses study interventions (but desires to continue with study observations)
3. Subject's BMI decreases to <5th percentile for age- and sex- (or <18.5 for those >20 years)

Subjects who are off study therapy will continue to be followed with collection of laboratory, radiographic, survey, and assessment data unless they meet the criteria for off study (see below).

For off-therapy patients, by family request and/or in response to questions during the assessments, routine clinical guidance for healthy diet and exercise will be provided by the PT and RD.

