14.0 ADVERSE EVENT REPORTING REQUIREMENTS

Adverse event (AE) data collection and reporting are required as part of every clinical trial to ensure the safety of patients enrolled in the studies as well as those who will enroll in future studies using similar agents. Adverse events are reported in a prescribed manner at scheduled times during the trial.

Induction chemotherapy has many associated toxicities due to the intensity of regimen, and these will be monitored per routine care by the treatment team and/or by the appropriate research team if the subject is enrolled on a concurrent therapeutic research study.

We will not record non-targeted toxicities (those described in clinical history Section 9.1) due to the underlying leukemia or treatment regimen.

As this trial consists of behavioral interventions (diet and exercise) that are within the scope of standard of care for patients, we will ONLY collect AE's that occur *during* or *immediately following* the exercise activities. If this should occur, the AE will be reported to the local IRB and the coordinating IRB (CHLA).

For an AE that occurs as above, we will record and report using the National Cancer Institute Common Terminology Criteria for Adverse Events v4.0 (CTCAE) available for download at <http://ctep.cancer.gov>.

All reporting of adverse events must include:

- severity (grade) of the event
- duration of the event
- attribution to the study (i.e. how the event is related to the study).
- whether hospitalization was necessary (or prolonged) for subjects

Categories of attribution in order of increasing likelihood are:

- Unrelated
- Unlikely
- Possible
- Probable
- Definite

All adverse events will be labeled "unexpected" for this behavioral study intervention.

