14.1 EXPEDITED REPORTING OF ADVERSE EVENTS

As a behavioral intervention that does not pose more than minimal risk to the subject, expedited reporting will only be required in the case:

Toxicities that occur during this protocol-specified activity (as described above) and cause or prolong hospitalization will be reported in an expedited manner to the IRB within 5 business days.

Toxicities that are \geq Grade 4 and occur during the protocol-specified activity (as described above) will be reported in an expedited manner to the IRB within 5 business days.

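### Adverse events are collected by exercise timing only, so events possibly related to the caloric deficit outside that window have no AE attribution or IRB-reporting route

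*Combined protocol and SAP*

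**What the plan says.** Section 6.1 describes one intervention with two parts, "aimed at creating a minimum 10% caloric deficit each day (10% nutritional + exercise) throughout the four weeks of induction therapy".

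Section 14.0 gives the reason for limited AE collection as "As this trial consists of behavioral interventions (diet and exercise) that are within the scope of standard of care for patients", and in the same sentence sets the limit: "we will ONLY collect AE's that occur" while the subject is exercising or straight afterwards. CTCAE v4.0 grading, the five-level attribution scale and reporting to the local and coordinating IRBs apply to an AE that meets that condition.

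Section 14.1 has two expedited triggers. One is "Toxicities that occur during this protocol-specified activity (as described above) and cause or prolong hospitalization". The other covers events of Grade 4 or higher that "occur during the protocol-specified activity (as described above) will be reported in an expedited manner to the IRB within 5 business days".

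On risk, Section 11.3 says "We do not anticipate any risks directly due to the dietary intervention". It goes on to say that subjects who cannot keep to the diet and/or the activity plan "may be at risk for psychological distress (i.e. depression, anxiety, etc".), and it provides for monitoring by the treatment team and psychosocial referral. Section 12.1 takes a subject off study therapy if "BMI decreases to <5th percentile for age- and sex" (with a limit of 18.5 for those over 20). Section 7.2 refers to this rule under modification of the dietary intervention.

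**The concern.** The collection rule follows exercise, which is intermittent, and gives no route of its own to the diet, which runs every day. The standard-of-care rationale is stated for both parts, so it does not explain why only one has an AE window.

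Section 13.3 presents the study as preparation for a randomized Phase III trial, and efficacy is compared with historical controls. With no concurrent arm, an excess of harm cannot be seen by comparing groups, so attribution of individual events carries more of the safety assessment. If diet-related events are not attributed, a report of no diet-related AEs says little about the diet, and the planners of the next trial could take it as reassurance.

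**Working it through.** The point rests on no alpha, power or rate, and the plan states no figure to reproduce. The check is to list the events that bear on the diet and see where each would go.

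| Event or measure | Where the plan captures it | AE attribution and IRB route |
|---|---|---|
| Syncope, fall or injury during or just after exercise | 11.3, 14.0 | Yes, whatever the cause |
| BMI fall below the off-therapy limit | 7.2, 12.1; follow-up data continue | None |
| Distress in subjects unable to adhere | 11.3: monitoring and referral | None |
| Weight, skin folds, waist-to-hip ratio, 24-hour recall | 9.1, every visit | None |
| Body fat and lean mass by DXA | 9.1, diagnosis and end of induction | None |
| PedsQL and CASP | 9.1, 13.4, four time-points | None |
| Time NPO, tube or parenteral feeding, ICU admission, osteonecrosis, fracture | 9.1, clinical history footnote | None |
| Grade 3 or 4 hepatic or pancreatic toxicity | 9.1, clinical history footnote (graded) | None |

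Only the first row enters the AE system, because of when the event occurs. The other rows are data without a judgement of relation to the intervention, unless an event happens to fall in the exercise window.

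**How narrow the window is (illustration).** Section 6.2.2 targets 200 minutes of exercise a week. A week has 7 × 24 × 60 = 10,080 minutes, so exercise at full adherence is 200/10,080 = 2.0%. The plan does not define how long the period after exercise lasts. Assume 15 to 60 minutes after each of 7 to 14 weekly sessions:
- shortest: (200 + 7 × 15)/10,080 = 305/10,080 = 3.0%;
- longest: (200 + 14 × 60)/10,080 = 1,040/10,080 = 10.3%.

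Under these assumptions about 90% to 97% of the week lies outside AE collection.

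**What collection could show (illustration).** Take 36 subjects, the evaluable target in Section 13.1, with full detection and independent events. The chance of at least one event at true rate p is 1 − (1 − p)^36. The documents give no rate, so p is assumed:
- p = 3%: 1 − 0.97^36 = 0.666, or 67%;
- p = 5%: 1 − 0.95^36 = 0.842, or 84%;
- p = 10%: 1 − 0.90^36 = 0.977, or 98%.

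If no event were seen, the one-sided 95% upper bound would be 1 − 0.05^(1/36) = 0.080, or 8.0%.

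**A related wording conflict.** Section 14.0 says that toxicities outside the targeted set, when due to the leukemia or its treatment, are not recorded. A parenthesis there points to the clinical history in Section 9.1. Read literally, it places the Section 9.1 items among those not recorded, whereas the Section 9.1 footnote lists them as part of the clinical history to be taken at each visit.

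**The case against.** The limit is a reasoned choice. The plan regards the intervention as behavioral, within standard of care and of no more than minimal risk. Induction toxicity is watched by the treatment team or a concurrent therapeutic study, and Section 16.0 adds ongoing monitoring by the study committee. Distress has a referral pathway, and Section 7.2 presents the BMI rule as a precaution for subjects at lower percentiles in a setting where fat gain is expected. With four-drug induction and no concurrent control, attributing weight loss, nausea or distress to the diet in a single patient would be weak.

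Much of this stands. It means that clinical oversight of the individual patient is not missing, and that attribution will be imprecise. It does not supply a route by which a diet-related event is judged, graded where needed and reported. An expectation of no direct dietary risk is also something the AE data should be able to test.

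Several stronger readings are tempting, and the documents do not support them:
- A reader might infer that a harm of the diet can never become an AE. The rule concerns timing and not cause, so a syncope to which under-nutrition contributed would be collected if it happened during exercise.
- A reader might infer that the study is bound to show no dietary harm. Weight, lean mass, nutrition support, ICU stays and QOL would all be visible as study data.
- A reader might infer that none of these data are graded. The hepatic and pancreatic items are.
- A reader might take the Section 14.0 parenthesis as proof that the Section 9.1 items go unrecorded. It is as plausibly a slip in wording, and it should be reconciled rather than used to discount those data.

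**Conclusion.** The concern holds in a limited form. Outside the exercise window, events possibly related to the caloric deficit are neither attributed to the study nor reported to the IRB as AEs. That includes the BMI-triggered stop and intervention-related distress, both of which the protocol provides for. The gap is in attribution and reporting, not in all data capture. Its consequence is that an absence of diet-related AEs would reflect the collection rule at least as much as the patients.

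This conclusion comes from the text alone. The percentages above only give scale. They rest on assumed rates, full detection and correct attribution, and on 36 evaluable subjects, although the number exposed could be larger. The change should be made, but the gap does not undermine the primary analysis.

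**What to change.** 1. In Section 14.0, collect AEs judged at least possibly related to either component, diet or exercise, throughout the intervention. Keep the existing exercise-window rule, and use the CTCAE grading and five-level attribution scale already specified.
2. Log BMI-triggered off-therapy events and intervention-related distress referrals on the AE form, with attribution. No clinical rule changes.
3. In Section 14.1, apply the existing five-business-day rule to diet-related events only when they meet its present thresholds: leading to or lengthening a hospital stay, or Grade 4 or higher. A BMI-triggered stop or a referral that meets neither is recorded but not expedited.
4. Reconcile the parenthesis in Section 14.0 with the clinical history footnote in Section 9.1, so that it is clear which toxicities are recorded.

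The cost is protocol wording and one form item at the weekly RD and PT contacts already planned in Section 6.1, with some added IRB reporting. The main downside is imprecise case-level attribution against background induction toxicity without a concurrent control. The report should say so when it presents the results.

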14.1 EXPEDITED REPORTING OF ADVERSE EVENTS

As a behavioral intervention that does not pose more than minimal risk to the subject, expedited reporting will only be required in the case:

Toxicities that occur during this protocol-specified activity (as described above) and cause or prolong hospitalization will be reported in an expedited manner to the IRB within 5 business days.

Toxicities that are \geq Grade 4 and occur during the protocol-specified activity (as described above) will be reported in an expedited manner to the IRB within 5 business days.

15.0 RECORDS AND REPORTING

Research records will be maintained through paper study-specific case reporting forms (CRF). Research records for this study will be maintained in locked cabinets in the Clinical Trials Office (CTO) or institutional research offices accessible only to the investigators and study team. The master list linking subjects to their unique identifier will be kept in the regulatory binder locked in the CTO office and in a password-protected database. Regulatory binder and CRFs will be maintained primarily by the research coordinator with assistance from the PIs/investigators as needed.

Study results will be entered by each site directly into the secure REDCap database maintained by USC/SC-CTSI. At conclusion of the treatment portion of the study, screening logs with coded identifiers only will be provided from each site to enable assessment of selection bias (e.g. CONSORT diagram). The database will then be downloaded by the study PI for potential further secondary analysis and follow-up as indicated in Section 13.2 (“Study Closure”). The database will remain under unique password-protection and will remain strictly confidential. At the conclusion of the prescribed 5-year follow-up period (final study closure), all identifying information will be destroyed and the database will be preserved in a password-protected completely de-identified format for a minimum of six years as per CCI requirements at which time it will be destroyed.

16.0 DATA AND SAFETY MONITORING PLAN

The Principal Investigators or designees will be available to answer questions of patients on the research protocol. As the study intervention constitutes a standard-of-care behavioral intervention only, data and safety monitoring for all patients enrolled on the study will be conducted by the study committee on an ongoing basis while the study is open.

